3.1 Eligibility Criteria

Rev. 11/17	_____ 3.1.1	Female patients presenting with initial diagnosis of any type of cancer, including patients with DCIS.
Rev. Add8	_____ 3.1.2	Patients must not have initiated chemotherapy, radiation therapy or endocrine therapy prior to registration to this study.
Rev. 11/17	_____ 3.1.3	Patients must not have had a prior hysterectomy, bilateral oophorectomy or sterilization of any method.
Rev. Add9	_____ 3.1.4	Patients must be pre-menopausal patients within the reproductive age range of 15-55 years. Please note, pre-menopausal will be defined as females meeting the following criteria: 
• Patients not currently on hormonal contraception with the presence of menses in the past 6 months.• If no menstruation in the past 6 months, without hormonal manipulation, then confirmed FSH < 23mIU/mL• If age < 47 years and on hormonal contraception, then patient will be eligible regardless of menstrual history• If age ≥ 47 years and on hormonal contraception, then FSH confirmed < 23mIU/mL
Rev. Add10	_____ 3.1.5	Pregnant females are eligible to participate in this study.
Rev. Add10	_____ 3.1.6	Patients must have the cognitive ability to participate in the study.

Rev. 11/17 4. CTEP Registration Procedures

Rev. Add8
Rev. Add11

Food and Drug Administration (FDA) regulations and National Cancer Institute (NCI) policy require all individuals contributing to NCI-sponsored trials to register and to renew their registration annually. To register, all individuals must obtain a Cancer Therapy Evaluation Program (CTEP) Identity and Access Management (IAM) account (<https://ctepcore.nci.nih.gov/iam>). In addition, persons with a registration type of Investigator (IVR), Non-Physician Investigator (NPIVR), or Associate Plus (AP) must complete their annual registration using CTEP's web-based Registration and Credential Repository (RCR) (<https://ctepcore.nci.nih.gov/rcr>).

RCR utilizes five person registration types.

- IVR — MD, DO, or international equivalent;
- NPIVR — advanced practice providers (e.g., NP or PA) or graduate level researchers (e.g., PhD);
- AP — clinical site staff (e.g., RN or CRA) with data entry access to CTSU applications (e.g., Roster Update Management System (RUMS), OPEN, Rave,);
- Associate (A) — other clinical site staff involved in the conduct of NCI-sponsored trials; and

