5.7.2 Patient Reported Outcomes Assessment Schedule

If a patient is eligible to participate in this study and the physician approves, the study is further discussed with the patient. Patients providing consent will be registered on trial. Participants will complete a total of 8 assessment visits (including baseline). Structured interviews will be administered to participants at the timepoints listed below. At each time point, two questionnaires will be administered by a study team member. Completion of these forms on a given visit should take about 10-20 minutes. Patient interviews are designed to assess the patient's reproductive health history, management and goals at baseline and as they progress through cancer treatment. Additionally, the Sexual Function Survey, which includes the PROMIS Sexual Function Brief Profile v1.0 – Female, is designed to assess sexual health at diagnosis and throughout treatment.

Patients will be assessed according to the following schedule:

Rev. Add8

Patient Baseline Interview (51 Questions)

Baseline

Patient Follow-Up Interview (34 Questions)

1. 3 Months from Baseline Visit
2. 6 Months from Baseline Visit
3. 12 Months from Baseline Visit
4. 24 Months from Baseline Visit

Patient Interview - During Chemotherapy/Radiation Treatment (11 Questions)

In addition to the above forms, each patient will complete the **Patient Interview During Chemo/Radiation Treatment** as well according to the following schedule:

Within one week prior to the start of each chemotherapy regimen for patients undergoing chemotherapy or every four weeks of RT for patients undergoing radiation therapy alone

Sexual Function Survey (16 Questions)

1. Baseline
2. Within one week prior to the start of each chemotherapy regimen for patients undergoing chemotherapy or every four weeks of RT for patients undergoing radiation therapy alone
3. 3 Months from Baseline Visit
4. 6 Months from Baseline Visit
5. 12 Months from Baseline Visit
6. 24 Months from Baseline Visit

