8.5.2 Stratum 2 with patients who are not pregnant, sexually active, and have completed childbearing

It is expected that intervention can increase the LTC usage rate at 6 months after baseline visit from 20% (without intervention) to 60% for patients in Stratum 2. Table 3 summarizes the power with various parameter values, assuming ICC=0.10, an exchangeable within-cluster correlation structure, t-distribution, and type I error rate at 0.10 (two-sided). As indicated in Table 3, this study needs an average of 5 eligible patients enrolled into stratum 2 per cluster in order to have 85% power to detect an improvement in the LTC usage rate at 6 months from 20% to 60%, assuming ICC=0.10, 8 institutions per arm, and CV=0.8.

Results from the fourth interim analysis suggest that approximately 40% of eligible patients can be categorized into Stratum 2 and the 6-month attrition rate is approximately 20%. With the stated 15 eligible patients to detect a change from 50% to 80% on the primary endpoint (assuming 8 sites per arm), the projected average cluster size is expected to be 4-5 eligible patients in stratum 2 ($=15 \times 0.4 \times 0.8$). Consequently, the new study design has at least 80% power to detect an increase from 20% to 60% in the LTC usage rate at 6 month between the two arms.

Table 3: Power for Various Plausible Parameter Values (assuming improvement from 20% to 60%, ICC=0.10, an exchangeable within-cluster correlation structure, t-distribution, and $\alpha=0.10$)

Number of Clusters (k, per arm)	Coefficient of Variation (CV)	Mean Cluster Size (m)	Power
8	0.5	3	0.71
	0.5	4	0.84
	0.5	5	0.89

Number of Clusters (k, per arm)	Coefficient of Variation (CV)	Mean Cluster Size (m)	Power
	0.5	10	0.97
	0.8	3	0.67
	0.8	4	0.80
	0.8	5	0.86
	0.8	10	0.95
10	0.5	3	0.79
	0.5	5	0.94
	0.5	10	0.99
	0.8	3	0.76
	0.8	5	0.92
	0.8	10	0.98

Rev. Add8 8.5.3 Stratum 3 with patients who are not pregnant and not sexually active
Stratum 3 is an observational group and no specific hypothesis is proposed for it.

Rev. Add10 8.5.4 Stratum 4 with pregnant patients and patients who are interested in becoming pregnant within one year of study enrollment.
Stratum 4 is an observational group and no specific hypothesis is proposed for it.

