8.6 Analysis Plan

8.6.1 Plan for the primary objective
With a cluster randomized design, the generalized estimating equations (GEEs) method will be used to evaluate the intervention effect. The GEEs method can be used to construct an extension of standard logistic regression²⁷. For the primary endpoint, appropriate reproductive health management, a GEE model with an exchangeable correlation structure (i.e., assuming every patient within a cluster is equally correlated with every other patient from that cluster) and registering institution as the cluster variable will be fitted to compare the rates between the intervention group and the no intervention group by combining patients in all strata. The appropriate reproductive health management rate at each time point will be summarized, by arm, with frequency and percentage along with its 95% confidence interval. This rate in the non-intervention arm will indicate whether reproductive health needs are adequately addressed (Hypothesis 1, Section [1.4.1](#)). Whether the intervention can improve reproductive health care (Hypothesis 2, Section [1.4.2](#)) can be determined by comparing this rate between the non-intervention arm and the intervention arm.

The same method will be used to evaluate the intervention effect on contraception usage for Stratum 1 and Stratum 2, separately. Since it is expected that contraception usage will be influenced by the number

of children (0, 1-2, >2), type of treatment (chemo vs. RT vs. surgery vs. combination), and disease stage (nonmetastatic vs. metastatic) as well, these factors will be included in the model as covariates. The contraception usage rate at each time point will be reported with frequency and percentage along with its 95% confidence interval. Similar analysis method will be applied to the proportion of patients with pregnancy by the end of 2 years after baseline visit on the study. The analysis will be applied to patients by stratum for each of these secondary endpoints.

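### The 6-month contraception model does not adjust for contraception use at baseline, a cheap loss of precision in the one LTC comparison the plan calls powered

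*Combined protocol and SAP*

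**What the plan says.** - **Model.** Section 8.6.1 fits a GEE extension of logistic regression to contraception usage, separately in Strata 1 and 2. It names three expected influences on usage (number of children, treatment type, disease stage) and says "as well, these factors will be included in the model as covariates". Baseline contraception use is not among them, and no comparison of new uptake is described.
- **Eligibility.** Section 3.1 states "Patients must not have had a prior hysterectomy, bilateral oophorectomy or sterilization of any method". It has no exclusion for current reversible contraception, and it expressly admits some current users: "If age < 47 years and on hormonal contraception, then patient will be eligible regardless of menstrual history".
- **Endpoint.** Section 8.5.2 expects the intervention to "increase the LTC usage rate at 6 months after baseline visit from 20% (without intervention) to 60% for patients in Stratum 2". This describes status at a time point. LTC is not spelled out, and section 8.1 places the endpoint details in Addendum II, which is not among the documents supplied.
- **Baseline data.** Section 5.7.2 says "Patient interviews are designed to assess the patient's reproductive health history, management and goals at baseline". Baseline use is therefore probably recorded, although the form itself is not supplied.
- **Power.** Section 8.5.1 concedes that Stratum 1 is underpowered. Section 8.5.2 claims at least 80% power for Stratum 2, "assuming ICC=0.10, 8 institutions per arm, and CV=0.8", with 4 to 5 women per cluster.

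**The concern.** The plan adjusts for factors because they are expected to influence usage, but omits prior status on the same variable, which is normally the strongest predictor of later status. A woman who enters with a method in place and keeps it would, on the natural reading of the endpoint, appear as a user at 6 months whichever arm her site is in.

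Nothing in the design balances this factor. The matched-pair randomisation was abandoned (section 8), and section 8.7 describes simple 1:1 allocation of institutions. With about 38 Stratum 2 women per arm in 8 unequal clusters, a sizeable chance difference in baseline use is ordinary. At stake are the precision of the Stratum 2 LTC comparison and how a reader should interpret it if the arms differ visibly at entry.

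**Working it through.** **1. The plan's own power (section 8.5.2, Table 3).** Inputs: 20% vs 60%, k = 8 per arm, CV = 0.8, ICC = 0.10, two-sided alpha 0.10, m = 5. Pooled variance, t with 14 df:
- L = m·ICC/(m·ICC + 1 − ICC) = 0.5/1.4 = 0.357
- DE = (1 + (m − 1)·ICC)/(1 − CV²·L·(1 − L)) = 1.4/0.853 = 1.641
- SE = √(2 × 0.24 × 1.641/40) = 0.140, so 0.40/SE = 2.850
- Power = T14(2.850 − 1.761) = 0.853, against 0.86 in Table 3 and 85% in the text. At m = 4 the same steps give 0.809, against 0.80.

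The m = 3 rows do not reproduce on any standard variant, and the calculator's exact algorithm is not given. Those rows do not bear on this point.

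**2. Chance imbalance in baseline use.** Mean Stratum 2 cluster size is 15 × 0.4 × 0.8 = 4.8, so n = 38.4 per arm. Using the more conservative design effect, DE = 1 + ((1 + 0.64) × 4.8 − 1) × 0.10 = 1.687. For baseline prevalence p, assumed to be 5% to 20% with the same ICC, SD = √(2p(1 − p) × 1.687/38.4).

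**3. Effect on the estimate.** Assume a share r = 0.90 of baseline users are still users at 6 months. To keep overall rates of 20% and 60%, uptake among non-users is u = (rate − rp)/(1 − p), and the pass-through in each arm is s = r − u. A 1-SD imbalance shifts the unadjusted difference by s(control) × SD if there is no effect. Under the planned effect it shifts it by the mean of the two slopes × SD.

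**4. Gain from adjustment, risk-difference scale.** Variance reduction = p(1 − p)(s²control + s²intervention)/(0.16 + 0.24). For p = 10%: 0.09 × (0.605 + 0.111)/0.40 = 0.161. Power is T14(2.850/√(1 − reduction) − 1.761); for p = 10%, T14(3.112 − 1.761) = 0.901.

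| p | SD of imbalance (points) | s control / intervention | Shift, no effect (points) | Shift, planned effect (points) | Variance reduction | Power at m = 5 |
|---|---|---|---|---|---|---|
| 5% | 6.5 | 0.737 / 0.316 | 4.8 | 3.4 | 8% | 0.876 |
| 10% | 8.9 | 0.778 / 0.333 | 6.9 | 4.9 | 16% | 0.901 |
| 20% | 11.9 | 0.875 / 0.375 | 10.4 | 7.4 | 36% | 0.954 |

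Simulation with variable cluster sizes gives reductions of about 8%, 15% and 38%. At 20% baseline use, the SD of the difference falls from 0.117 to 0.091. Varying continuation from 80% to 100% widens the extremes to 5% and 50%.

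**5. What one realisation can do.** Take no effect, p = 10% and full continuation, so u = 0.10/0.90 = 0.111 and s = 0.889. The outcome variance given baseline use is 0.16 − 0.09 × 0.889² = 0.0889, and DE/n cancels. The false-positive rate of the unadjusted test is then:
- no imbalance: 2Φ(−1.761 × √(0.16/0.0889)) = 2Φ(−2.363), about 2%
- 1-SD imbalance: about 7%
- 1.645-SD imbalance: about 19%

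Averaged over randomisations it stays near the nominal 10%.

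**6. Adding the covariate to the logistic GEE.** In 300 simulated trials at 20% baseline use and 90% continuation (the three planned covariates left out for simplicity), the model with baseline use gave no usable estimate in about 41%, against 1% to 2% without it. Where both fitted, the median SE of the log odds ratio rose from 0.53 to 0.84, and the estimate itself moved from 1.77 to 2.78 because the conditional odds ratio is a different quantity. The cause is sparse data: the expected number of baseline users per arm is 38.4 × 0.20 = 7.7, 38.4 × 0.10 = 3.8 or 38.4 × 0.05 = 1.9. The planned model already carries 8 parameters (intercept 1, arm 1, children 2, treatment 3, stage 1) on about 77 women.

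**The case against.** The strongest reply is that this is a preference about precision, not a flaw in validity. Randomisation makes the unadjusted comparison unbiased, its interval already allows for chance imbalance, and this is a secondary endpoint on which the sample size does not rest. That stands, and it sets the level of the recommendation.

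Four stronger readings are tempting, and the documents do not support them:
- **Women using LTC at entry are counted as 6-month successes.** This is the natural reading of a usage rate, but the definition is in Addendum II. If LTC includes sterilisation, that component is new by construction, since prior sterilisation is excluded. The eligibility text speaks of hormonal contraception, which is not the same category as LTC.
- **Imbalance passes straight into the result.** It passes in part: 0.63 to 1.00 in the control arm and 0.21 to 0.50 in the intervention arm over the range examined. The programme might also affect continuation, so baseline users are not wholly uninformative.
- **The imbalance is systematic.** Patients do enrol after their site's arm is assigned (sections 4.1 and 5.1), so it need not be only chance. Nothing supplied shows that selection on contraception occurred.
- **One more covariate in the planned model would narrow the interval.** On the log-odds scale it did not.

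It is also fair that sections 8.6.1 and 8.6.2 promise usage rates at each time point and summaries of baseline and follow-up assessments, so a baseline difference could be displayed. Displaying it is not the same as adjusting for it.

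**Conclusion.** The omission is real and rests on current text: the covariate list lacks baseline use, reversible-method users are not excluded, and the endpoint is worded as usage at 6 months. The consequence is limited. A 1-SD chance imbalance of about 6 to 12 points would move the unadjusted difference by about 3 to 9 points under the planned 40-point effect, or 4 to 12 points if there is no effect. These shifts are ordinary in size and average to zero.

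A suitable adjustment would cut the variance of the risk difference by about 8% to 40%. Where in that range depends mainly on how much of the 20% control rate is existing use. Baseline prevalence (5% to 20%), continuation (80% to 100%, with 90% in the table) and the ICC of baseline use (0.10) are assumptions; the documents give none of them. With a baseline ICC of 0 the imbalance SD falls to roughly 5 to 9 points.

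This is a cheap improvement to a secondary analysis, conditional on Addendum II not already restricting the endpoint to new use.

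**What to change.** First check Addendum II. If the LTC endpoint there still includes women using LTC at entry:
- For Stratum 2, prespecify a between-arm risk difference in 6-month LTC use standardised on baseline LTC use (or an identity-link or penalised model), with cluster-robust inference.
- State the fallback if an arm has few or no baseline users: report the unadjusted comparison together with the non-user analysis below.
- Tabulate baseline LTC use by arm.
- Report, as a supporting result, new LTC uptake at 6 months among women not using it at baseline.

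Do not simply add the term to the logistic GEE. Before finalising, confirm that the Patient Baseline Interview records current LTC use.

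The cost is a little extra programming, sparse-data handling and one or two tables. No new visits, patients or data items should be needed if the interview already captures the variable.

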8.6.2 Plan for secondary objectives

Rev. 5/17

Objective 1: To assess the degree of discrepancy between patients and their clinicians in estimates of significance of the reproductive health goals for the patient.

Assume the rating (1-10) on the reproductive health value questions is on a continuous scale. For each question, mean and standard deviation in terms of rating will be computed by arm for patients and their clinicians, respectively. The difference in ratings between the patient and his/her clinician will also be computed and summarized with descriptive statistics. The ratings between patients and clinicians will be compared using a linear mixed-effect model. Only data available from both the patient and his/her clinician will be included in this part of analysis. This analysis can address Hypothesis 3 that patients and clinicians have different perspectives regarding reproductive health objectives of females with cancer (Section [1.4.3](#)).

Objective 2: To evaluate baseline and follow-up reproductive health assessments.

Frequency/percentage will be used to summarize results collected at each time point. Longitudinal analysis will be applied when appropriate.

Objective 3: To identify clinical and demographic factors predictive of the adequacy of reproductive health management.

To identify clinical and demographic factors predictive of the adequacy of reproductive health management (Hypothesis 4, Section [1.4.4](#)), the GEE method will be used.

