1.4 Hypotheses

- 1.4.1 The reproductive health needs for females with cancer are not adequately assessed and addressed by cancer care providers.
- 1.4.2 The implementation of the proposed reproductive health assessment and algorithm will optimize the reproductive health objectives of females with cancer.
- 1.4.3 Patients and clinicians have different perspectives regarding reproductive health objectives of females with cancer.
- 1.4.4 There are certain clinical, demographic, healthcare delivery, and socioeconomic factors that affect patients with regards to adequacy of reproductive health management.

Rev. Add9

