2.2 Secondary Objectives

- 2.2.1 To assess the degree of discrepancy between patients and their clinicians in estimates of significance of the reproductive health goals for the patient
- 2.2.2 To evaluate baseline and follow-up reproductive health assessments for trends in reproductive health choices relating to oncofertility, oncocontraception and pregnancy over the 2 year study period
- 2.2.3 To identify clinical and demographic factors that predict the adequacy of reproductive health care management

Rev. Add11

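### The only inferential analysis for the patient-clinician discrepancy objective appears to compare mean ratings; within-pair differences are only described, with no interval or agreement measure

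*Combined protocol and SAP*

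**What the plan says.** Section 2.2 gives the objective as "To assess the degree of discrepancy between patients and their clinicians in estimates of significance of the reproductive health goals for the patient". The related hypothesis in section 1.4 is "Patients and clinicians have different perspectives regarding reproductive health objectives of females with cancer".

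Section 8.6.2, Objective 1, plans the following for each question:

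- Scale: "Assume the rating (1-10) on the reproductive health value questions is on a continuous scale".
- Group summaries: "mean and standard deviation in terms of rating will be computed by arm for patients and their clinicians, respectively".
- Within-pair differences: "The difference in ratings between the patient and his/her clinician will also be computed and summarized with descriptive statistics".
- Inference: "The ratings between patients and clinicians will be compared using a linear mixed-effect model".

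Only complete patient-clinician pairs enter. The section closes: "This analysis can address Hypothesis 3 that patients and clinicians have different perspectives regarding reproductive health objectives". It does not give the model's fixed or random effects, a significance level, the descriptive statistics to be reported, an agreement index, or a criterion for the hypothesis.

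**The concern.** The objective is a pair-level quantity: the distance between a patient's rating and the rating her own clinician gives for her. A comparison of ratings by role estimates something else, the average signed difference. The two part company when errors run in both directions. If some clinicians rate a goal well above the patient and others well below, the average difference can be near zero while most pairs are far apart. Conversely, a small shift shared by nearly all pairs can be highly significant while every pair is close.

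What is at stake is the conclusion drawn from Objective 1. A null model could be reported as agreement, or a significant one as large disagreement, and neither follows. The signed differences carry the missing information only if their spread is reported, and the plan does not say that it will be.

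**Working it through.** The plan gives no sample size, power or effect size for this objective, so there is no figure to reproduce. The check is of what the test can and cannot detect.

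**Inputs**

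- Scale 1 to 10, treated as continuous (8.6.2).
- Number of pairs: not stated for this objective. Range used: 240 (eligible patients required, 8.3); 425 (projected accrual, 8.4); and 425 × 0.95 × 0.85 = 343, which applies the 5% ineligibility and 15% attrition of 8.3.
- Two-sided alpha 0.05: assumed. At the 0.10 used for the primary endpoint, null rejection rates would be about 10%.
- Rating distributions: assumed, uniform on 1 to 10.

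**Step 1. What is tested.** Let D be the patient's rating minus the clinician's. With complete pairs and a random intercept per pair, the role effect is the mean of D, and the test is t = mean(D) / (SD(D)/√n), provided the intercept variance is not estimated at zero. If the expected mean of D is zero, the rejection rate stays at alpha whatever n is.

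**Step 2. Extreme case.** Half the pairs rate (1, 10) and half (10, 1). D is −9 or +9, so the mean is 0 while the mean absolute difference is 9, the maximum possible.

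**Step 3. Four patterns.** The first three have equal means.

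- *Unrelated ratings:* the variance of one rating is (10² − 1)/12 = 8.25. So SD(D) = √(2 × 8.25) = 4.06, mean |D| = (10² − 1)/(3 × 10) = 3.30, and the share at least 4 apart is 2 × (6+5+4+3+2+1)/100 = 42%.
- *Opposite ratings* (clinician = 11 − patient): |D| takes the values 9, 7, 5, 3, 1, each with probability 0.2. Mean |D| = 5.00, SD(D) = √33 = 5.74, and 60% are at least 4 apart.
- *Close agreement* (never more than 1 apart, no net shift): simulated mean |D| = 0.60, SD(D) = 0.77.
- *Near-uniform shift* (never more than 1 apart): simulated mean |D| = 0.90, SD(D) = 0.30.

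Paired t-test, 4,000 simulated trials per cell:

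| Pattern | Rejected, n = 240 | n = 343 | n = 425 | Mean abs. difference | At least 4 apart |
|---|---|---|---|---|---|
| Unrelated | 5.1% | 5.0% | 5.0% | 3.30 | 42% |
| Opposite | 5.3% | 5.1% | 4.7% | 5.00 | 60% |
| Close | 5.2% | 4.8% | 4.7% | 0.60 | 0% |
| Shift | 100% | 100% | 100% | 0.90 | 0% |

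The mean test treats the first three alike and flags the fourth. The pair-level measures separate them.

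**Step 4. Check with a fitted mixed model.** A random-intercept model rejected in 6% of 200 simulated trials for unrelated ratings at n = 240 (simulation error √(0.06 × 0.94/200) = 1.7 points). The opposite pattern needs a caveat. Ratings within a pair are then negatively correlated, so the intercept variance would be set to zero. The model would take the variance of D as 16.5 instead of 33, and the rejection rate would be P(|Z| > 1.96 × √0.5) = P(|Z| > 1.386), about 17%. That is an inflated false-positive rate for a mean shift that is still zero, so it does not measure discrepancy either.

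**Step 5. Milder illustration.** For normal D with mean 0, mean |D| = SD × √(2/π), and P(|D| ≥ 3) = 2 × (1 − Φ(3/SD)).

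- SD 3: 3 × 0.798 = 2.4 points; 2 × (1 − Φ(1)) = 32%.
- SD 2: 2 × 0.798 = 1.6 points; 2 × (1 − Φ(1.5)) = 13%.

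**The case against.** Five things can be said for the plan.

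- **Within-pair differences are computed and described.** A usual summary includes the SD, which separates the patterns above (0.77 for close agreement, 4.06 for unrelated, 5.74 for opposite). Limits of agreement are only the mean ± 1.96 SD of the same differences. This stands in part: two-sided disagreement would probably be visible. But the statistics are not named, no interval is planned, and nothing says how they bear on the conclusion.
- **Hypothesis 3 can be read at group level.** It names patients and clinicians as two groups, and for a systematic difference between them a mixed model is a suitable test. This stands. It does not make the model a measure of the distance between pairs, which section 2.2 asks for.
- **The model's terms are not given.** That it tests a mean shift is an inference, though the natural one, and reported variance components could inform agreement. Section 8.1 also places endpoint details in Addendum II, which is not among the documents available here.
- **The mean absolute difference exceeds zero from rating noise alone.** A test of whether it is above zero would nearly always support Hypothesis 3. This stands, and the fix avoids that use.
- **Nothing suggests that errors balance on any particular question.** True; the illustrations show what the test can miss, not what is likely.

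A reader might also infer that the plan lets the mean comparison decide Hypothesis 3, so that the hypothesis could be wrongly rejected. The documents do not support this. Section 8.6.2 says only that the analysis can address the hypothesis, sets no decision rule, and may mean the whole Objective 1 analysis. Hypothesis 3 is the alternative, so a null result fails to support it and does not reject it.

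**Conclusion.** The point holds as a mismatch between a pair-level objective and an inferential step that, on its natural reading, tests average bias. If over- and under-estimates balance, that step does not measure disagreement, and more pairs do not help. A trivial common shift, by contrast, is detected with certainty in the simulated example. The size under assumed normal differences with mean 0 is an undetected mean absolute difference of 2.4 points (32% of pairs at least 3 apart) at SD 3, or 1.6 points (13%) at SD 2. These SDs, the uniform ratings and alpha 0.05 are assumptions; the documents give no data on the spread.

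The planned description of paired differences softens the problem without resolving it. This is a minor improvement to a secondary objective. The primary endpoint and the sample size are not touched.

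**What to change.** In section 8.6.2, Objective 1:

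1. For each question, make a pair-level measure the main result for the degree of discrepancy: the mean absolute paired difference, with the limits of agreement or the share of pairs differing by at least a pre-specified number of points.
2. Give confidence intervals that allow for clustering by clinician and institution.
3. Keep the mixed model, state its fixed and random effects, and label it as the test of systematic over- or under-estimation, that is, the group-level reading of Hypothesis 3.
4. State that a null result from that model is not evidence of agreement.
5. Do not use an absolute difference greater than zero as the test of Hypothesis 3.

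The ratings and the pairing are already collected, so no visit, form or patient is added. The cost is one more table per question and the choice of a threshold, if the share of discrepant pairs is used, before the ratings are analysed.
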